10 SAFETY, EFFICACY EVALUATIONS, BLOOD SAMPLE COLLECTION AND TESTING, AND SAFETY MEASUREMENTS

Study procedures and their timing are summarized in the Schedule of Assessments (Appendix 1). All scales and tasks will be completed and/or administered by qualified and trained site raters who meet the training requirements and qualifications of the scale or task standards set by the Sponsor and training vendors.

10.1 EFFICACY MEASURES

10.1.1 UNIFIED PARKINSON'S DISEASE RATING SCALE

The UPDRS is well-established and the most widely used assessment to quantify the signs and symptoms of PD (Fahn, Elton, & Committee, 1987). The total UPDRS consists of 4 parts which assess the following:

1. Mentation, behavior and mood
2. Activities of Daily Living (ADL)
3. Motor function
4. Complications of therapy

Only Part III will be utilized in this trial. The UPDRS Part III is a 14-item rating scale, which consists of the motor examination. Each item is scored from 0 (Normal) to 4 (Most severe). The UPDRS Part III scale should only be administered by a rater who has adequate experience with subjects with PD and should be a trained neurologist or other trained research staff with experience in conducting the UPDRS. All attempts should be made to ensure that the same trained research staff member performs the UPDRS part III for a given subject.

An additional single item to rate dyskinesia is added to the scale and is rated from 0 (No dyskinesia) to 4 (Severe dyskinesia: maximal amplitude and present during most of the exam).

The UPDRS and dyskinesia rating will be conducted as indicated in the Schedule of Assessments (Appendix 1).

10.2 SAFETY MEASURES

Investigators are responsible for monitoring the safety of subjects who have entered this study and for alerting the Sponsor or its designee to any event that seems unusual, even if this event may be considered an unanticipated benefit to the subject.

The Investigator is responsible for the appropriate medical care of subjects during the study.

The Investigator remains responsible for following, through an appropriate health care option, AEs that are serious or that caused the subject to discontinue before completing the study. The subject should be followed until the event is resolved or explained. Frequency of follow-up evaluation is left to the discretion of the Investigator.

10.2.1 ADVERSE EVENTS

An AE is any sign, symptom, illness, clinically significant abnormal laboratory value or ECG finding, or other untoward medical occurrence associated with the use of an investigational product that appears or worsens in a subject during a clinical study. This definition does not imply a causal relationship between the AE and the investigational product.

Adverse events beginning with the initial dose of investigational product or during the subsequent duration of their enrollment in the study will be considered treatment-emergent AEs (TEAE). TEAEs will be recorded on the AE CRF to include the event, date of onset, severity, frequency, seriousness, date of resolution, action taken with respect to the AE (e.g., concomitant medication, non-pharmacological treatment, etc.), outcome, and relationship to the investigational product. All TEAEs related to study drug will be followed through resolution or 30 days after the subject terminates from the study, whichever occurs first.

Medical conditions present or AEs occurring prior to the first dose of investigational product will be captured as medical history in the CRF. Any AE occurring during the study that is related to a pre-existing condition or event that worsens in intensity or frequency after the first dose of investigational product will be recorded as a TEAE.

Lack of drug effect is not an AE in clinical studies because the purpose of the clinical study is to establish drug effect.

10.2.2 CLASSIFICATION OF AN ADVERSE EVENT

10.2.2.1 SEVERITY OF EVENT

Each AE will be assessed by the Investigator with regard to the categories discussed in the sections below. The Investigator will assess all AEs for severity in accordance with the following standard ratings.

MILD = of little concern to the subject and/or of no clinical significance; is not expected to have any effect on the subject's health or well-being;

MODERATE = discomfort enough to cause interference with or change in usual activities; is likely to require medical intervention and/or close follow-up;

SEVERE = incapacitating or unable to work or participate in many or all usual activities, is of concern to the subject and/or poses substantial risk to the subject's health or well-being; is likely to require medical intervention and/or close follow-up.

For an AE that begins and ends on the same day and severity worsens over that day, one AE will be recorded and will be assessed with the highest level of severity for that day. For an AE that continues over multiple days (past the initial day of onset), if an increase in severity level occurs, only the maximum level of severity will be documented. For a non-TEAE in which the duration continues beyond administration of the first dose of study drug, if the AE increases in severity or frequency after study drug administration, then the initial AE will be closed and a new TEAE

will be opened documenting the new higher level of severity (at the maximum severity level for the remaining duration of the AE). An AE characterized as intermittent requires documentation of onset and duration of each episode.

10.2.2.2 RELATIONSHIP TO STUDY DRUG

The Investigator will assess the causality/relationship between study drug and the AE. One of the following categories should be selected based on medical judgment, considering the definitions below and all contributing factors:

Related	A clinical event, including laboratory test abnormality, occurs in a plausible time relationship to study drug administration and which concurrent disease or other drugs or chemicals cannot explain. The response to withdrawal of the study drug should be clinically plausible.
Probably Related	A clinical event, including laboratory test abnormality, is a known effect of drug with a reasonable time sequence to administration of the drug, and which cannot be reasonably explained by the known characteristics of the participant's clinical state.
Possibly Related	A clinical event, including laboratory test abnormality, with a reasonable time sequence to administration of the study drug, but which could also be explained by concurrent disease or other drugs or chemicals. Information on treatment withdrawal may be lacking or unclear.
Unlikely Related	A clinical event, including laboratory test abnormality, with a temporal relationship to study drug administration which makes a causal relationship improbable and in which other drugs, chemicals, or underlying disease provide plausible explanations.
Not Related	A clinical event, including laboratory test abnormality, with little or no temporal relationship with study drug administration. Typically explained by extraneous factors (e.g., concomitant disease, environmental factors, or other drugs or chemicals)

10.2.3 OVERDOSE

In the event of an overdose of study drug, the Investigator should use clinical judgment in treating the overdose and contact the Sponsor-designated Medical Monitor, or designee. The Investigator should refer to the relevant document(s) for detailed information regarding warnings, precautions, contraindications, AEs, and other significant data pertaining to the study drug. Such documentation may include, but not be limited to the Investigator's Brochure. As the study drug will only be administered by study staff while the subject is in the clinic, the likelihood of an overdose occurring in this study is considered unlikely.

10.2.4 PREGNANCY

Any pregnancy that occurs from baseline after study drug exposure until study completion must be reported to the Sponsor-designated Medical Monitor on a Pregnancy Notification Form within 24 hours of learning of its occurrence.

Each pregnancy must be reported as well to the Sponsor-designated Medical Monitor within 24 hours of learning of its occurrence. The pregnancy must be followed up to determine outcome (including premature termination) and status of mother and child.

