1 SYNOPSIS

Name of Investigational Study Product: BTRX-246040	
Title of Study: Phase 2a, Double-blind, Placebo-Controlled Study to Investigate the Safety, Tolerability, Pharmacokinetics, and Efficacy of BTRX-246040 in Parkinson's Disease Subjects with Motor Fluctuations	
Approximate Number of Planned Subjects: 24 subjects or 3 cohorts of 8 subjects each	Phase of Development: 2a
Length of Study: Treatment Duration is 1 day and total duration of the study is up to 36 days including the 28-day screening period	
Study Objective: The purpose of this study is to assess the safety, tolerability, pharmacokinetics and efficacy of BTRX-246040 in subjects with PD who have motor fluctuations and predictable early morning off periods. Safety Objectives 
• To evaluate the safety of single ascending doses of BTRX-246040 in PD subjects with motor fluctuations and predictable early morning off periods Tolerability Objectives 
• To assess the tolerability of BTRX-246040 in PD subjects with motor fluctuations and predictable early morning off periods  Efficacy Objectives: 
• To evaluate the effect of single ascending doses of BTRX-246040 on the clinical features of Parkinson's disease in levodopa-treated PD subjects with motor fluctuations and predictable early morning off periods	

Study Population:

Levodopa-responsive Parkinson's disease subjects with motor fluctuations and predictable morning OFF periods.

Study Design:

The study will consist of 3 sequential, single ascending dose cohorts of 8 subjects each with a 6:2 randomization to BTRX-246040 or placebo. The planned dosing for each cohort will be 40, 80, and 120 mg. After enrollment of the first cohort has been completed, doses for subsequent cohorts may be modified based on a review of the available data (safety, tolerability, efficacy, and PK) by an unblinded Dosing Review Committee (DRC). A similar review and determination of dosing for the subsequent cohort will be performed after completion of each cohort and based on all data available from previous cohorts.

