Placebo will be administered orally at the same number of capsules as active drug at each Cohort. Placebo capsules will consist of inactive ingredients and look identical to BTRX-246040.

Planned Duration of Treatment:

Study drug will be administered once on Day 1

Criteria for Evaluation:

Safety: Will be assessed descriptively by adverse events reporting which will include AEs, SAEs, vital signs, laboratory values, physical and neurological exams, C-SSRS, and ECGs.

Tolerability: Will be assessed by percent who complete protocol

Pharmacokinetics: Descriptive review of Pharmacokinetic (PK) ██████████
███████████

Efficacy: Will be assessed descriptively for the following endpoints.

Primary Endpoint:

- Maximal change in UPDRS Part III from pre-dose to post-dose on Day 1

Secondary Endpoints:

- Duration of ON time on Day 1
- Percentage of subjects that turn ON on Day 1
- Time to ON on Day 1

- Area under the curve for UPDRS Part III during the 8 hours of assessment on Day 1
- Change from pre-dose dyskinesia rating (from the UPDRS Part III motor response and dyskinesia assessment)

Statistical Methods:

All data will be assessed descriptively as presented in the SAP, and no formal statistical comparisons will be performed.

Sample Size Calculation:

Formal sample size calculation will not occur. A sample size of 8 subjects per group is deemed sufficient to evaluate the preliminary safety, tolerability, and efficacy of the different dose levels.

TABLE OF CONTENTS

1	Synopsis.....	2
Table of Contents.....		8
2	Protocol Signature Page.....	14
3	Abbreviations.....	15
4	Introduction	18
5	Objectives.....	21
5.1	Primary Objective	21
6	Investigational Plan.....	22
6.1	Summary of Study Design	22
6.2	Study Design and Control.....	23
7	Study Population	24
7.1	Inclusion Criteria.....	24
7.2	Exclusion Criteria.....	25
7.2.1	Rationale for Exclusion of Certain Subjects	27
7.3	Discontinuations	27
7.3.1	Early Discontinuation.....	27
7.3.2	Discontinuation of the Study.....	28
8	Study Procedures.....	29
8.1	Visit 1: Screening.....	29
8.2	Visit 2: Treatment Period (Day 1).....	30
8.3	Visit 3: Safety Follow-up (Day 8 ±1)	31
8.4	Early Termination Visit	32
9	Treatment.....	33
9.1	Treatments Administered.....	33

9.2 Materials and Supplies.....	33
9.3 Method of Assignment to Treatment.....	33
9.4 Rationale for Selection of Doses in the Study.....	33
9.5 Selection and Timing of Doses.....	34
9.6 Blinding	35
9.7 Dosing Review Committee	35
9.8 Concomitant Therapies.....	35

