7.1 INCLUSION CRITERIA

Subjects are eligible to be included in the study only if they meet **all** the following criteria:

1. Diagnosed with Parkinson's disease (consistent with the UK PD Society Brain Bank Criteria for the Diagnosis of PD)
2. Men or women ≥ 30 years old and ≤ 76 years old
3. Female subjects must be either surgically sterilized or 2 years post menopausal at screening
4. Modified Hoehn and Yahr scale ≤ 3 in the ON state
5. Montreal Cognitive Assessment (MoCA) Score ≥ 26
6. Currently has a clear and decisive response to levodopa, and receiving a stable dose of levodopa (at least 4 doses per day of levodopa or ≥ 3 doses per day of RytaryTM (Carbidopa and levodopa Extended-Release Capsules) for at least four weeks prior to screening)
7. Experiencing motor fluctuations during waking hours with at least 2 hours of OFF periods each day, including predictable early morning OFF periods, based on subject assessment
8. Able to participate in the study in the practically defined OFF state
9. All anti-parkinsonian medications maintained at a stable dose for at least 4 weeks prior to the initial Screening Visit with the exception of MAO-B inhibitors, which must be maintained at a stable level for at least 8 weeks prior to the screening visit
10. Approved by a central Enrollment Authorization Committee as meeting entry criteria and being a suitable candidate for the study
11. Male subjects agree to use a reliable method of birth control during the study and for at least 90 days following the last dose of BTRX-246040 or placebo.
12. Informed and given ample time and opportunity to think about his/her participation in this study and has given his/her written informed consent on an Institutional Review Board (IRB) or Independent Ethics Committee (IEC) approved consent form
13. Judged to be reliable and able to keep all appointments for clinic visits, tests, and procedures, including venipuncture, and examinations required by the protocol.

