8.3 VISIT 3: SAFETY FOLLOW-UP (DAY 8 ±1)

All randomized subjects will return to the clinic for a final safety visit approximately 7 days after the last dose of study drug.

The following assessments will be performed at the follow-up visit (see Schedule of Assessments [Appendix 1] for details):

1. Collection of concomitant medications.
2. Vital signs (BP and pulse both supine and standing, respiratory rate, temperature), and weight
3. C-SSRS – since last visit version
4. QUIP-RS since last visit version
5. Physical and neurological examinations
6. 12-lead ECG
7. Safety laboratory assessment (including clinical chemistry panel, hematology, coagulation [including PT, aPTT, INR] parameters and urinalysis)

8. Collection of AEs.

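### Pregnancy reporting ends at an undefined study completion, about a week after the dose for each subject on the likelier reading, while male contraception runs at least 90 days and partners are not named

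*Protocol*

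**What the plan says.** - **Reporting window (Protocol 10.2.4):** "Any pregnancy that occurs from baseline after study drug exposure until study completion must be reported". The section adds that "Each pregnancy must be reported as well to the Sponsor-designated Medical Monitor within 24 hours of learning of its occurrence" and asks for the outcome to be followed for both mother and child. It does not mention partners of male subjects.
- **Women (Protocol 7.1, item 3):** "Female subjects must be either surgically sterilized or 2 years post menopausal at screening".
- **Men (Protocol 7.1, item 11):** the condition reads "use a reliable method of birth control during the study and for at least 90 days following the last dose of BTRX-246040", and it applies equally to men given placebo.
- **Dosing (Protocol synopsis):** "Study drug will be administered once on Day 1".
- **End of participation:** the synopsis says that "total duration of the study is up to 36 days including the 28-day screening period". Section 8.3, headed Day 8 ±1, says that "All randomized subjects will return to the clinic for a final safety visit approximately 7 days after the last dose of study drug".
- **SAEs, for comparison (Protocol 10.2.5):** collected for 30 days after the last dose, and after that only if the investigator judges them related to the product or a procedure. A congenital anomaly is one of the listed SAE outcomes.

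**The concern.** Item 11 treats the weeks after the dose as a period in which conception should be avoided, and its wording separates the study itself from the 90 days that follow. Section 10.2.4 ties reporting to study completion. If that is the subject's last visit, the duty to report new pregnancies lapses about a week after dosing, while the contraception requirement has nearly twelve weeks still to run. For example, a site applying the first sentence of 10.2.4 literally would have no clear duty to report a partner pregnancy conceived on Day 20.

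The stake is safety information. Pregnancies after paternal exposure, and their outcomes, could go unrecorded for most of the period that the protocol marks out. A report of no pregnancies would then say little about that period. Because women who could conceive are not enrolled, it also matters that sites are never told whether partner pregnancies count.

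**Working it through.** **1. Where a subject's study completion falls.** The inputs are the 28-day screening period and the total duration (synopsis), and the final visit on Day 8 ±1 (section 8.3).

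28 screening days + Day 1 to Day 8 = 28 + 8 = 36 days.

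This reproduces the stated maximum of 36 days and puts a subject's completion at Day 8. Section 7.3.1 supports this reading, since it uses study completion in the name of a form filled in for the individual subject.

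**2. Share of the contraception period covered, subject-level reading.** There is one dose, on Day 1. Days covered = day of final visit − 1. Share = days covered ÷ 90.

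| Final visit | Days after dose | Share of 90 days | Days not covered |
|---|---|---|---|
| Day 7 | 7 − 1 = 6 | 6/90 = 6.7% | 90 − 6 = 84 |
| Day 8 | 8 − 1 = 7 | 7/90 = 7.8% | 90 − 7 = 83 |
| Day 9 | 9 − 1 = 8 | 8/90 = 8.9% | 90 − 8 = 82 |

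Item 11 says at least 90 days, so these shares are upper limits. They are shares of calendar days, not of expected pregnancies.

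**3. Trial-level reading.** The three cohorts are sequential, with a Dosing Review Committee review after cohorts 1 and 2 (section 6.1). If study completion means the end of the trial, subjects in the early cohorts have a longer window. Its length cannot be computed because the protocol gives no enrolment timeline. For the last subject dosed, the trial ends with that subject's final visit, so the window is again 6 to 8 days.

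**4. Comparison with the SAE window.** 30/90 = 33.3%. On the subject-level reading, pregnancy reporting stops earlier than routine SAE collection, and that collection itself leaves 90 − 30 = 60 days of the contraception period.

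**5. Occurrence against recognition.** The window in 10.2.4 depends on when the pregnancy occurs, and the 24-hour clock starts when the site learns of it. A conception on Day 3 learned of on Day 40 is therefore reportable, while one on Day 20 is not clearly so. The schedule of assessments (Appendix 1) plans no contact after Visit 3 through which a site would learn of either.

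**The case against.** A reader might infer that the rule captures practically no exposed pregnancies, or that the trial is bound to report none. The documents do not support that. Whether a pregnancy would be recognised by Day 8 does not decide whether it is reportable, because the rule turns on occurrence. What stands is weaker: nothing is scheduled that would prompt a late report.

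A reader might also infer that partners are excluded. They are not. The sentence covers any pregnancy, and following mother and child fits a partner well, especially as enrolled women are not expected to conceive. What stands is that sites have to work this out for themselves.

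Further points on the other side:

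- **Day 8 is an inference.** Study completion is undefined. The subject-level reading is better supported, but the trial-level one is possible. An undefined end point for a mandatory report is itself a reason to amend.
- **The second sentence of 10.2.4 has no end date.** Read alone, it could require reporting indefinitely. It follows the sentence that sets the window and offers no window of its own, so it does not clearly close the gap. If it was meant to be open-ended, the section disagrees with itself.
- **SAE reporting gives partial cover.** A congenital anomaly judged related stays reportable without limit. Its application to a partner's child is not explicit, and it records neither the pregnancy nor a normal outcome.
- **No strict contradiction.** Item 11 is an eligibility condition and 10.2.4 a reporting rule. Nothing says the two periods must match, and item 11 gives no rationale. This is accepted: the point is a mismatch to reconcile, not a proven error. The Investigator's Brochure and consent form are not available, and the consent form may already instruct men about partners.
- **Small numbers.** Eighteen subjects (3 × 6) are planned to receive active drug, ages run from 30 to 76, and men agree to contraception. Few events are to be expected.

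**Conclusion.** The concern holds as a gap in the wording of safety reporting. On the subject-level reading, section 10.2.4 covers 6 to 8 of at least 90 post-dose days and leaves 82 to 84 in which a new pregnancy is not clearly reportable. On the trial-level reading, the gap shrinks by an unknown amount for early cohorts and stays about the same for the last subject dosed. On either reading the section does not name the group in which pregnancies could practically arise.

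The day counts rest on a Day 1 dose, a final visit on Day 7 to 9, and 90 days as the shortest contraception period. They need no assumption about when a pregnancy is recognised. The number of pregnancies that might be missed cannot be estimated from the protocol and is probably small. Efficacy endpoints and their analysis are unaffected.

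**What to change.** Reconcile section 10.2.4 with inclusion criterion 11:

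1. Replace the undefined end point with a window that runs from study drug administration to the end of the protocol's own 90-day period, and make the section's second sentence subject to the same window.
2. State that the rule covers pregnancies in partners of male subjects.
3. At the Day 8 visit, tell male subjects to report a partner pregnancy to the site through that date, with outcome follow-up subject to the partner's consent.

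The cost is protocol and consent wording and a partner-consent form. Sites keep a passive reporting channel open for another 82 to 84 days, about 12 weeks. No visit or procedure is added, and dosing and treatment rules do not change.

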10.2.5 SERIOUS ADVERSE EVENTS

A serious adverse event (SAE) is any AE that results in one of the following outcomes, regardless of the Investigator's opinion of causation:

1. death
2. initial or prolonged in-subject hospitalization
 - a. Surgeries planned prior to signing the ICF will not be considered SAEs. However, worsening of the underlying medical condition during the study will be considered an AE and must be captured as serious if any SAE-defining outcomes occur as a result.
3. a life-threatening experience (that is, immediate risk of dying)
4. persistent or significant disability/incapacity
5. congenital anomaly/birth defect
6. other medically important serious event as determined by the Investigator (for example, an AE that jeopardizes the subject and may require medical or surgical intervention to prevent one of the outcomes listed in this definition). If a subject experiences an SAE after signing informed consent, but prior to receiving investigational product, the event will be captured as medical history in the CRF and not submitted as reportable-event unless the Investigator feels the event may have been caused by a protocol procedure.

SAEs reported after a subject has taken a dose of investigational product will be collected in the pharmacovigilance system for 30 days after the last dose of investigational product. Thereafter, only SAEs that the Investigator feels were related to the investigational product or a protocol procedure must be reported.

All SAEs must be captured on a study-specific SAE form in addition to the AE CRF. Study site personnel must alert the Sponsor-designated Medical Monitor of the SAE and must submit the completed study-specific SAE form to the Sponsor-designated Medical Monitor within 24 hours of the site's awareness of the SAE.

The Investigator and supporting personnel responsible for subject care should discuss with the Sponsor-designated Medical Monitor or designee any need for supplemental investigations of

SAEs. The results of these additional assessments conducted must be reported to the Sponsor-designated Medical Monitor. If a subject death occurs during participation in the study and a post-mortem examination is performed and a copy of the autopsy report is available, it should be submitted to the Sponsor-designated Medical Monitor.

The Investigator is responsible for safety reporting in compliance with their Institutional Review Board (IRB).

